**T2.0**

**Is the proposed research study limited to the inclusion of deceased individuals?**

\* No

**T2.1**

**Are any research activities being conducted at the VA Pittsburgh Healthcare System or with VA funds?**

\* No

[\[reviewer notes~\]](#)

**T3.0**

**What is the anticipated risk to the research participants?**

Minimal Risk

**T3.1**

**Why do you feel that all aspects of this research study, including screening and follow-up, involve no more than minimal risk to the research subjects?**

Trans-cutaneous Electrical Nerve Stimulation (TENS) devices are FDA approved and commercially available to treat a variety of clinical conditions including pain (migraines, musculoskeletal pain and labor pain). The only reported side-effects are local irritation from electrode pads and minor cramping of stimulated muscles. Many studies have evaluated the use of TENS devices for parasacral neuromodulation in children with no serious adverse events reported.

The voltage used for the TENS device will be only as high as is required to stimulate an involuntary muscle contraction of at least two toes. In various trials in adults this voltage very rarely corresponds to any actual discomfort to the patient. If during the trial stimulation at the time of enrollment in the office, the child demonstrates an intolerance to this stimulation due to discomfort, he/she will be excluded from the study.

**T4.0**

**Does the proposed study qualify for 'exempt' IRB review or for a determination of either 'not research' or 'no human subject' involvement?**

\* No

**T5.0**

**Does the proposed research study qualify for 'expedited' IRB review status?**

\* No

[\[reviewer notes-\]](#)

**CS1.0 What is the reason for this submission?**

New Research Protocol Submission

**CS1.1 Has this research study been approved previously by the University of Pittsburgh IRB?**

\* No

**CS1.1.1 Has this research study (or a substantially similar research study) been previously disapproved by the University of Pittsburgh IRB or, to your knowledge, by any other IRB?**

\* No

[\[reviewer notes-\]](#)

**CS2.0 Title of Research Study:**

**Foot Neuromodulation for Nocturnal Enuresis in Children**

**CS2.0.1**

**Requested approval letter wording:**

**CS2.1 Research Protocol Abstract:**

Background: Previous animal model studies at the University of Pittsburgh have shown a significant impact on inhibiting bladder overactivity and increasing bladder capacity with neuromodulation techniques, specifically tibial nerve stimulation. This has been translated into adult clinical trials through the department of urology. Through the use of a commercially available subcutaneous nerve stimulator placed on the dorsum of the foot, we were able to demonstrate a significant increase in bladder capacity and the delay of voiding sensation for up to 5 hours after stimulation in eight healthy subjects. This prompted the clinical trial approved under IRB PRO13020474 which is currently enrolling patients.

The incidence of night-time overactive bladder leading to nocturnal enuresis (bedwetting) is very common in the pediatric and teenage population, particularly in patients without daytime bladder overactivity symptoms. When behavioral modification (i.e. refraining from night-time fluid consumption and bladder irritants, and bedwetting alarms for timed voiding) fails which it often does there is a paucity of effective and safe treatment options. Medications can be tried, but generally these are from the tricyclic antidepressant family and carry significant side effects limiting their use.

Aim: We aim to utilize the same technology currently being studied under IRB PRO13020474 for pediatric patients with nocturnal enuresis, taking advantage of the possible increase in bladder capacity and inhibited bladder activity to potentially help children stay dry at night. Electrical stimulation will be applied to the foot via skin surface electrodes for a minimum of 1

hour before bed for 2 weeks to 25 subjects. Subjects will be required to keep a daily log indicating the number of night-time incontinent voids. Subjects will also be asked to complete a validated questionnaire prior to treatment, during the two week treatment phase and two weeks after treatment. The primary outcomes of this study are improvement in the average number of night-time incontinent voids measured by daily log and subjective symptom improvement based on questionnaire comparison at the three phases of the study. Subjects who feel they are having a positive response to TENS treatment and would like to continue participation in the study for an additional 6 weeks may do so.

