**2.3 Summarize the general classification (e.g., descriptive, experimental) and methodological design (e.g., observational, cross-sectional, longitudinal, randomized, open-label single-blind, double-blind, placebo-controlled, active treatment controlled, parallel arm, cross-over arm) of the proposed research study, as applicable.**

This is an experimental, open-label study. Both the subject and the investigator will be informed about the foot stimulation. The results obtained before and after the treatment will be compared in the same subject.

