**2.17 What are the main outcome variables that will be evaluated in this study?**

1) Number of night-time incontinent episodes per two week period comparing baseline number of voids (first two weeks of study), number during two-week stimulation period (weeks 3-4), and number during two-week after-stimulation period (weeks 5-6).

2) Subjective quality of life measures as recorded by validated quality of life questionnaire prior to study start, after week 4 and after week 6 to evaluate for any differences.

3) For the subjects who continue participation for an additional 6 weeks, we hope to prove long-term efficacy and sustainability in symptom relief, and to ensure no unanticipated adverse outcomes with continued usage

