**2.18 Describe the statistical approaches that will be used to analyze the study data.**

\* Addressed below:

The data will be statistically analyzed using student t-test and ANOVA

[\[reviewer notes~\]](#)

**2.19 Will this research be conducted in (a) a foreign country and/or (b) at a site (e.g., Navajo Nation) where the cultural background of the subject population differs substantially from that of Pittsburgh and its surrounding communities?**

\* No

Note that copies of training records, licenses, certificates should be maintained in the study regulatory binder and are subject to audit by the Research Conduct and Compliance Office (RCCO).

In addition, individuals planning to conduct human subject research outside the United States must complete an optional module on the CITI training website: International Studies. [Click here](#) to access the instruction sheet for accessing optional CITI modules.

[\[reviewer notes~\]](#)

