**3.10 What is the total number of subjects to be studied at this site, including subjects to be screened for eligibility?**

Note: The number below is calculated by summing the data entered in question 3.11. Any additions or changes to the values entered in 3.11 will be reflected in 3.10.

\* 40

**3.11 Identify each of the disease or condition specific subgroups (include healthy volunteers, if applicable) that will be studied.**

Click on the "Add" button and specify for each subgroup:

1) how many subjects will undergo research related procedures at this site; and

2) if applicable, how many subjects will be required to undergo screening procedures (e.g., blood work, EKG, x-rays, etc.) to establish eligibility. **Do Not include subjects who will undergo preliminary telephone screening.**

\*

Subgroup	Number to undergo research procedures	Number to undergo screening procedures
View Pilot study of tibial nerve stimulation	25	40

**3.12 Provide a statistical justification for the total number of subjects to be enrolled into this research study at the multicenter sites or this site.**

\* Described below:

This is a pilot study to determine if foot stimulation has any effect on nocturnal enuresis. The study is designed through the use of an objective night-time voiding log and subjective quality of life questionnaires to determine the effect of foot stimulation. As the variations on these symptom parameters is unknown, it is difficult to to determine the total number of subjects based on statistical analysis. Therefore, we decided on 25 subjects in this pilot study. Once statistical significance is reached , we will stop recruiting additional subjects in order to maintain the subject number at a minimum.

[\[reviewer notes~\]](#)

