3. The investigators will monitor the progress of the study and the efficacy of the treatment after collecting data from the first 10 subjects. Any unexpected adverse effect will be addressed immediately and reported to the IRB committee. In addition to the monitoring of every 10 subjects, an annual review of the study will also be conducted to assure the experimental design, identify any unexpected adverse effects for reporting, and review the progress of subject recruitment

4. The data will be locked in the urology office by the investigators for safety and privacy. An annual review of the safety and privacy of the data will be performed. If any problem occurs, it will also be addressed immediately during any time of the year.

5. The following will be reported to IRB annually: a list of persons who monitored the data

and safety; the date when the monitoring/review occurs; a summary of any problems detected; final decisions about changes of the study based on the annual review.

6. The potential adverse events may be reported to IRB including:

Use of TENS stimulator: Foot skin irritation, redness, or rash, or foot cramp.

[reviewer notes~]

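### Two unranked primary outcomes over three phases, with no stated significance level, primary contrast or adjustment: at an assumed 0.05 per test the false-positive rate is about 8–23% before any interim look

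*Combined protocol and SAP*

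**What the plan says.** CS2.1 gives two primary outcomes in one sentence: "The primary outcomes of this study are improvement in the average number of night-time incontinent voids measured by daily log and subjective symptom improvement". Neither is placed ahead of the other.

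Section 2.17 lists both as main outcome variables over three phases. The voiding log is analysed by "comparing baseline number of voids (first two weeks of study), number during two-week stimulation period (weeks 3-4", and then by the fortnight after stimulation. The questionnaire is scored "prior to study start, after week 4 and after week 6 to evaluate for any differences". Section 2.6 gives each outcome two questions: an effect during treatment and a residual effect afterwards.

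The design (2.3) is open-label and within-subject: "The results obtained before and after the treatment will be compared in the same subject". The whole of the analysis plan in 2.18 reads "The data will be statistically analyzed using student t-test and ANOVA". It gives no significance level, sidedness, primary contrast, order of outcomes or adjustment.

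Section 3.12 sets 25 subjects without a calculation and adds: "Once statistical significance is reached , we will stop recruiting additional subjects". It does not say which outcome, comparison or level is meant. Section 5.13, item 3, adds that "The investigators will monitor the progress of the study and the efficacy of the treatment after collecting data from the first 10 subjects", and refers to monitoring of every 10 subjects.

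**The concern.** With two outcomes of equal standing, each read at more than one time point, the plan supports between two and six primary tests. Any of them could be reported as the finding, because nothing fixes in advance which one answers the study question. The total chance of a false-positive result is then above the level used for each test.

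This does not depend on interim analysis. It remains if all 25 children are analysed once. It matters more here because 3.12 makes statistical significance the reason to stop recruiting and says that the study is to determine whether stimulation has any effect. If the result that counts can be chosen afterwards, a chance finding on one outcome in one window could be carried forward as evidence that the device works.

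**Working it through.** **The plan's own figure.** There is none to reproduce: no level, power or calculated sample size is given.

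**Inputs from the documents.** Two primary outcomes (CS2.1); three phases each (2.17); t-test and ANOVA (2.18); within-subject comparison (2.3); maximum of 25 subjects (3.12); efficacy review after 10 subjects and every 10 (5.13), read as looks at 10, 20 and 25.

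**Assumptions not in the documents.** Two-sided 0.05 per test; normal data; correlation between phases 0.5 to 0.7; correlation between the two outcomes 0.3 to 0.7 unless stated.

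**Step 1: ceiling if the tests were independent.** The chance of at least one false positive in k tests is 1 − (1 − 0.05)^k.

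- k = 2: 1 − 0.95² = 9.75%
- k = 4: 1 − 0.95⁴ = 18.5%
- k = 6: 1 − 0.95⁶ = 26.5%

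**Step 2: allow for correlation.** Contrasts that share a baseline are correlated. With equal variance σ² and equal phase correlation w, the two contrasts against baseline have covariance σ²(1 − w) and variance 2σ²(1 − w) each. Their correlation is therefore 0.5 whatever w is, so the result hardly depends on the assumed phase correlation. Simulated null trials give, for at least one p < 0.05:

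| Tests on each of the two outcomes | One analysis at 25 | Looks at 10, 20, 25, either outcome may stop |
|---|---|---|
| One contrast (stimulation vs baseline) | 8–10% | 17–20% |
| One repeated-measures ANOVA | 8–10% | 17–20% |
| Stimulation and post vs baseline | 15–18% | 29–33% |
| All three pairwise | 20–23% | 37–42% |

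The 18% in the third row is for unrelated outcomes. Widening the outcome correlation to 0–0.8 moves the limits by only one or two points (14–18%, 19–23% and, with looks, 16–43% overall).

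**Step 3: direction.** The outcomes are defined as improvement. Counting only significant results in the direction of benefit, one analysis gives 4–5% with two tests and 7–9% with four; with looks, 8.5–10% and 15–17%.

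**Step 4: other readings of the stopping sentence**, with looks at 10, 20 and 25 and one contrast or ANOVA per outcome. If only the log can stop recruitment, the false-positive rate is 10–11% on the log and 14–15% on either outcome. If both must be significant, the chance of at least one false positive at the stop is about 10%.

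**Step 5: what the fixes achieve.**

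- Holm on two stimulation-versus-baseline tests, one analysis: an error occurs when the smaller p-value is below 0.025. For independent tests this is 1 − 0.975² = 4.9%; with correlated outcomes, 4–5%.
- One contrast at 0.05 at each of the three looks: about 10%.
- One contrast at 0.022 at each of the three looks: about 5%.

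**The case against.** A reader might infer that significance on any of the outcomes ends recruitment, at an unadjusted 5%, so that the error rate is several times 5%. The documents do not support that as a statement of the plan. No level is given anywhere, so 5% is an assumption. Section 3.12 leaves the trigger open; it does not say that any one result suffices. The two outcomes alone give about twice 5%. Going well beyond that needs several contrasts per outcome, the looks in 5.13, or both.

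The case against goes further. ANOVA is the natural test for three phases, and one ANOVA per outcome gives only 8–10%. The 15–23% figures need pairwise t-tests not gated by an ANOVA, which 2.18 does not say will be run. Section 2.6 gives each window a role, and Aim 1 in 1.2 is the log. Comparing post-stimulation with stimulation is not described as a test of treatment effect. About half of the errors would be towards worsening. And this is a self-described pilot with no control arm.

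Most of this stands as a limit on size, and the ranges above reflect it. It does not remove the point. Section 2.18 names t-tests beside ANOVA without making one depend on the other. The roles in 2.6 create two questions per outcome and do not choose between them, and numbering the aims does not rank outcomes that CS2.1 calls primary together. Pilot status lowers the stakes, but 3.12 still makes significance decide when recruitment ends.

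**Conclusion.** The concern holds as a specification gap with a measurable consequence. Significance level, primary outcome, primary contrast and stopping trigger are all undefined. At an assumed two-sided 0.05 per test and one analysis of 25 children, the chance of at least one false-positive result is about 8–10% on the narrowest reading, 15–18% if both the acute and the residual question are tested on both outcomes, and 20–23% if all pairs are tested. Roughly half of these results would favour the device.

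The 17–42% range applies only if the reviews in 5.13 are used as unadjusted looks and either outcome may stop recruitment. That added inflation belongs to the stopping rule. It should be changed, with weight suited to a pilot.

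**What to change.** In CS2.1, 2.17 and 2.18, name one primary contrast: the change in wet-episode rate from the baseline fortnight to the stimulation fortnight (Aim 1), tested once at two-sided 5% after the final subject. Make the questionnaire and all post-stimulation comparisons secondary, reported with confidence intervals and without a claim of effect. If both outcomes must stay primary, apply Holm to the two stimulation-versus-baseline tests.

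In 3.12, delete the sentence that stops recruitment at significance. If it stays, tie it to that one contrast with a level adjusted for the looks, about 0.022 per look at 10, 20 and 25. Naming the contrast while testing at 5% at each look would still err at about 10%, and Holm across outcomes does not correct for looks.

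The windows must also be settled: 2.6 places stimulation in the second and third weeks, while 1.2 and 2.17 place it in the third and fourth. These passages need to be reconciled before the contrast can be written down.

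The cost is wording in these sections. The questionnaire loses its stand-alone primary claim or, under Holm, each outcome faces a slightly stricter level. Deleting the stopping sentence gives up a possible early end, at most 25 − 10 = 15 subjects if the first look is at 10.

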**CS2.2 Select the category that best describes your research:**

[\[reviewer notes~\]](#)

**CS3.9 Is this your first submission, as PI, to the Pitt IRB?**

\* No

[\[reviewer notes~\]](#)

**CS8.0 Select the entity responsible for scientific review.**

**Department Review** - (a dean, department chair, division chief, or center head)

Note: **DoD funded studies** require departmental review

**CS8.1 Select the school, department or division which is responsible for scientific review of this submission.**

[U of Pgh | School of Medicine | Urology](#)

[\[reviewer notes~\]](#)

**CS9.0 Does this research study involve the administration of an investigational drug or an FDA-approved drug that will be used for research purposes?**

\* No

**CS10.0 Is this research study being conducted under a University of Pittsburgh-based, sponsor-investigator IND or IDE application?**

\* No

*If YES, you are required to submit the IND or IDE application and all subsequent FDA correspondence through the Office for Investigator-Sponsored IND and IDE Support*

(O3IS). Refer to applicable University policies posted on the O3IS website ([www.O3IS.pitt.edu](http://www.O3IS.pitt.edu)).

[\[reviewer notes-\]](#)

**CS11.0 Use the 'Add' button to upload one or more of the following:**

- the sponsor protocol (including investigator initiated studies) and/or other brochures
- the multi-center protocol and consent form template, *if applicable*

Name Modified Date

**Is this research study supported in whole or in part by industry? This includes the provision of products (drugs or devices).**

\* No

**Is this a multi-centered study?**

\* No

[\[reviewer notes-\]](#)

**CS12.0 Does your research protocol involve the evaluation or use of procedures that emit ionizing radiation?**

\* No

**CS13.0 Does this research study involve the deliberate transfer of recombinant or synthetic nucleic acid molecules into human subjects?**

\* No

Upload Appendix M of NIH Guidelines:

Name	Modified Date
------	---------------

**CS14.0 Are you using UPMC facilities and/or UPMC patients during the conduct of your research study?**

\* Yes

If Yes, upload completed Research Fiscal Review Form:

Name	Modified Date
Fiscal Review	8/26/2014 8:24 AM

[\[reviewer notes-\]](#)

**CS15.0 Indicate the sites where research activities will be performed and/or private information will be obtained.**

Choose all sites that apply and/or use **Other** to include sites not listed:

Sites:

UPMC

**UPMC**

Sites:

UPMC Children's Hospital

If you selected **School**, **International** or **Other**, list the sites:

**\*For research being conducted at non Pitt or UPMC sites, upload a site permission letter granting the researcher permission to conduct their research at each external site:**

Name Modified Date

**CS15.1 Have you, [name], verified that all members of the research team have the appropriate expertise, credentials, and if applicable, hospital privileges to perform those research procedures that are their responsibility as outlined in the IRB protocol?**

\* Yes

**CS15.2 Describe the availability of resources and the adequacy of the facilities to conduct this study:**

\* We have previously been awarded a \$25,000 grant from the Society of Urodynamics, Female Pelvic Medicine and Urogenital Reconstruction (SUFU) which we will use for the purchase of equipment (neuromodulators and subcutaneous foot pads). Subjects will be enrolled in the urology outpatient clinics at the Children's Hospital of Pittsburgh. We anticipate have adequate resources to enroll subjects and perform all necessary study tasks.

[reviewer notes~]

**CS16.0 Special Research Subject Populations:**

Categories

Children (age < 18 years old)

[\[reviewer notes-\]](#)**CS17.0 Does your research involve the experimental use of any type of human stem cell?**\*  No[\[reviewer notes-\]](#)**NIH Definition of a Clinical Trial**

***A research study in which one or more human subjects are prospectively assigned to one or more interventions (which may include placebo or other control) to evaluate the effects of those interventions on health related biomedical or behavioral outcomes.***

 See Common Rule definition of research at [45 CFR 46.102\(d\)](#) .

 See Common Rule definition of human subject at [45 CFR 46.102\(f\)](#) .

 The term "prospectively assigned" refers to a pre-defined process (e.g., randomization) specified in an approved protocol that stipulates the assignment of research subjects (individually or in clusters) to one or more arms (e.g., intervention, placebo, or other control) of a clinical trial.

 An intervention is defined as a manipulation of the subject or subject's environment for the purpose of modifying one or more health-related biomedical or behavioral processes and/or endpoints. Examples include: drugs/small molecules/compounds; biologics; devices; procedures (e.g., surgical techniques); delivery systems (e.g., telemedicine, face-to-face interviews); strategies to change health-related behavior (e.g., diet, cognitive therapy, exercise, development of new habits); treatment strategies; prevention strategies; and, diagnostic strategies.

 Health-related biomedical or behavioral outcome is defined as the pre-specified goal(s) or condition(s) that reflect the effect of one or more interventions on human subjects' biomedical or behavioral status or quality of life. Examples include: positive or negative changes to physiological or biological parameters (e.g., improvement of lung capacity, gene expression); positive or negative changes to psychological or neurodevelopmental parameters (e.g., mood management intervention for smokers; reading comprehension and /or information retention); positive or negative changes to disease processes; positive or negative changes to health-related behaviors; and, positive or negative changes to quality of life.

**CS18.0 \* Based on the above information, does this study meet the NIH definition of a clinical trial?** Yes  No

If Yes, click Save and then [Click Here For Study Team's CITI Training Records](#) . Please ensure all personnel's training is up to date

[\[reviewer notes-\]](#)

- 1.1 Objective: What is the overall purpose of this research study?** (Limit response to 1-2 sentences.)  
To determine the effects of electrical stimulation of the nerves in the foot on the incidence of nocturnal enuresis (bedwetting) in children.
- 1.2 Specific Aims: List the goals of the proposed study (e.g., describe the relevant hypotheses or the specific problems or issues that will be addressed by the study).**  
Aim #1: To determine if foot stimulation can decrease nocturnal enuresis in children as measured by daily night-time voiding log.  
  
Aim #2: To determine if foot stimulation can improve quality of life questionnaire scores during a 6-week period, with foot stimulation applied during the third and fourth week, as measured by a validated quality of life survey.  
  
Aim # 3: Subjects who feel they are having a positive response to TENS treatment and would like to continue participation in the study for an additional 6 weeks may do so. By collecting this data for an extended period of time we hope to prove long-term efficacy and sustainability in symptom relief, and to ensure no unanticipated adverse outcomes with continued usage
- 1.3 Background: Briefly describe previous findings or observations that provide the background leading to this proposal.**  
Previous animal model studies at the University of Pittsburgh have shown a significant impact on inhibiting bladder overactivity and increasing bladder capacity with neuromodulation techniques, specifically tibial nerve stimulation ([name] et al, 2011). This has been translated into adult clinical trials through the department of urology. Through the use of a commercially available subcutaneous nerve stimulator placed on the dorsum of the foot, we were able to demonstrate a significant increase in bladder capacity and the delay of voiding sensation for up to 5 hours after stimulation in eight healthy subjects (Chen et al, 2014). This prompted the clinical trial approved under IRB PRO13020474 which is currently enrolling patients.  
  
The incidence of night-time overactive bladder leading to nocturnal enuresis (bedwetting) is very common in the pediatric and teenage population, particularly in patients without daytime bladder overactivity symptoms. When behavioral modification (i.e. refraining from night-time fluid consumption and bladder irritants, and bedwetting alarms for timed voiding) fails which it often does there is a paucity of effective and safe treatment options. Medications can be tried, but generally these are from the tricyclic antidepressant family and carry significant side effects limiting their use.  
  
Various clinical trials abroad have studied the impact of transcutaneous parasacral nerve stimulation as well as percutaneous tibial nerve stimulation for overactive bladder in children with promising results (Sillen et al, 2014; Barroso et al, 2013; DeGannaro et al 2011; Loredelo et al 2010; Malm-Buatsi et al 2007). These studies have shown good efficacy and child tolerability with nerve stimulation in a more invasive approach than we are attempting with transcutaneous foot stimulation.
- 1.4 Significance: Why is it important that this research be conducted? What gaps in existing information or knowledge is this research intended to fill?**  
Nocturnal Enuresis is a very common and difficult to treat problem in the pediatric population which can have significant negative impact on a child's quality of life. Apart from medications which can have significant side effects limiting their use, there is a lack of effective and safe treatment options for children with frequent nocturnal enuresis. If foot

stimulation prior to bed does indeed improve the frequency of nocturnal enuresis, it may provide a safe and non-invasive therapeutic option.

For subjects the would like to continue participation in the study for an additional 6 weeks, we would like to explore how durable of a response we can achieve with a longer stimulation period

[\[reviewer notes~\]](#)

**2.1 Does this research study involve the use or evaluation of a drug, biological, or nutritional (e.g., herbal or dietary) supplement?**

\* No

[\[reviewer notes~\]](#)

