#### Questionnaire:

Subjects will complete the quality of life questionnaire attached to this application at the start of the study (prior to week 1) to establish a baseline, after the second week of treatment period (week 4 of study) to determine a treatment effect, and after the sixth week to determine any residual post-treatment effect.

The subjects can call or email the investigators anytime during the 6-week at-home test for questions or any problems encountered. At the end of the 6-week study, the subjects are asked to return the stimulator and night-time voiding log to the investigator's office.

Subjects who feel they are having a positive response to TENS treatment and would like to continue participation in the study for an additional 6 weeks may do so. We will ask that they continue to keep their logs and answer the questionnaires

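### Aim 3 and main outcome 3 seek to prove lasting efficacy and ensure no unanticipated harm from an uncontrolled extension that only self-judged responders enter; section 1.4's exploratory wording is all this design supports

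*Combined protocol and SAP*

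**What the plan says.** Section 1.2, Aim #3, offers the extension to "Subjects who feel they are having a positive response to TENS treatment and would like to continue participation in the study" for a further 6 weeks, and gives its purpose as "By collecting this data for an extended period of time we hope to prove long-term efficacy and sustainability in symptom relief". Section 2.17 lists this among the main outcome variables: "we hope to prove long-term efficacy and sustainability in symptom relief, and to ensure no unanticipated adverse outcomes with continued usage". That item names no variable, time window or comparison period.

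Other parts of the document are more modest. Section 1.4 says "we would like to explore how durable of a response we can achieve with a longer stimulation period". Section 3.12 calls the study a pilot. The abstract (CS2.1) confines the primary outcomes to the log and the questionnaire over the three core phases and presents the extension as an option.

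Section 2.3 describes an open-label study and states one principle of comparison: "The results obtained before and after the treatment will be compared in the same subject". Section 2.3.1 confirms that there is no placebo arm. The whole analysis plan in section 2.18 is "The data will be statistically analyzed using student t-test and ANOVA", and no test is assigned to the extension.

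Section 2.6 has continuing families keep up the logs and questionnaires. It sets no threshold for a positive response and does not say when families decide. The same section says "At the end of the 6-week study, the subjects are asked to return the stimulator and night-time voiding log", and section 2.11 gives total participation as 6 to 12 weeks, which fits an extension added after week 6.

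**The concern.** Two features of the extension prevent a conclusion about efficacy: it has no control group, and children enter because they or their families believe it is working.

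Wet nights over two weeks vary by chance. A family that compares weeks 3-4 with weeks 1-2 and sees a fall will more often have a child whose baseline count was unluckily high, or whose weeks 3-4 count was luckily low, or both. In the extension both drift back to that child's usual level. The extension then looks better than weeks 1-2 and worse than weeks 3-4, with no treatment effect at all. Section 2.17 does not say which comparison counts.

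If the wording is followed as it stands, outcome 3 could report sustained benefit that selection alone could produce, and an event-free extension could be read as showing that continued use causes no unanticipated harm.

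**Working it through.** **Inputs from the documents.** At most 25 children (3.12); two-week baseline and stimulation logs (2.6), with stimulation in weeks 3-4 as dated in 2.17; a 6-week extension; eligibility of at least 4 episodes a month (3.13), about 14 × 4/30.4 = 1.8 wet nights per 14. The figure of 25 cannot be reproduced, because section 3.12 gives no alpha, power, effect or SD and says "As the variations on these symptom parameters is unknown". Everything below on wetting rates and entry rules is therefore assumed.

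**Model, no treatment effect.** Child i has a constant nightly probability p_i. Weeks 1-2: B ~ Binomial(14, p_i). Weeks 3-4: T ~ Binomial(14, p_i). Extension per two weeks: E ~ Binomial(42, p_i)/3. Among continuers:
- apparent fall below baseline = (mean B − mean E)/mean B
- apparent worsening against weeks 3-4 = (mean E − mean T)/mean T

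**Worked example**, p_i from a Beta distribution with mean 0.5 and concentration 8 (true mean 7.0 wet nights per 14):

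| Who continues | B | T | E | Against weeks 1-2 | Against weeks 3-4 |
|---|---|---|---|---|---|
| T below B (about 10.5 of 25) | 8.17 | 5.83 | 7.00 | 1.17/8.17 = 14% better | 1.17/5.83 = 20% worse |
| Noisy: probability 0.8 if T below B, otherwise 0.3 | 7.49 | 6.53 | 7.00 | 0.49/7.49 = 7% better | 0.47/6.53 = 7% worse |
| T of 3 or fewer (level only) | 3.96 | 2.25 | 3.97 | about 0 | 1.72/2.25 = 76% worse |
| Random half | 7.00 | 7.01 | 7.00 | about 0 | about 0 |

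**Range over five assumed populations** (1,000,000 children each). Three respect the eligibility floor: p_i = 4/30.4 + (1 − 4/30.4) × Beta(1,2), Beta(1,1) or Beta(3,1.5), with means of 5.9, 7.9 and 9.9 wet nights per 14. Two are low-rate: Beta(1,6) and Beta(0.5,3), mean 2.0. Noisy entry means B − T + N(0, SD) > 0 with SD 2 or 4.

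| Entry judged on weeks 3-4 | Fall below weeks 1-2: three floor-respecting cases | All five cases | Against weeks 3-4, all five |
|---|---|---|---|
| Unrelated to the log | about 0% | about 0% | about 0% |
| T at or below the median | about 0% | about 0% | about 8-124% worse |
| Noisy change | 4.1-10.9% | 4.1-17.3% | 4.4-26.9% worse |
| Exact: any drop, or at least 25% lower | 9.5-19.7% | 9.5-30.9% | about 13-71% worse |

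If families decide after week 6 (mean of weeks 3-4 and 5-6 in place of T), noisy entry gives a fall of 4.2-18.3% below baseline, hence the rounded 4-18%. The worsening against weeks 3-4 is then 2.2-13.0%.

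**Safety.** With zero events in n children, the one-sided 95% upper limit for the true rate is 1 − 0.05^(1/n). For n = 25: 1 − 0.05^0.04 = 11.3%. For n = 10 (an assumed number of continuers): 1 − 0.05^0.1 = 25.9%.

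**The case against.** The strongest reply is that this is largely wording. The text says only that the investigators hope to prove efficacy, the study calls itself a pilot, the abstract keeps the extension out of the primary outcomes, and sections 3.5.5 and 5.12 say benefit is not known or guaranteed. All of that is true, and it limits the weight of the point. It does not remove it: section 2.17 still lists the claim as a main outcome, and a hope to prove still names proof as the target.

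A second reply is that the bias is hypothetical. A reader might infer that the extension will look falsely favourable, or that outcome 3 carries a false-positive rate near one half. The documents support neither. A simulated paired t-test against baseline is favourable in about 22-48% of null trials under exact entry on weeks 3-4, but section 2.18 assigns no such test to the extension, and the baseline comparator is itself inferred from section 2.3. Sustainability and durability point at least as naturally to weeks 3-4, where selection works against the treatment. The two low-rate populations supply the upper ends of the percentage ranges and put 57% and 62% of children below the eligibility floor. Low-rate populations that respect the floor reach similar upper ends, but a mean as low as 2.0 would then need nearly every child at the minimum.

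On safety, *ensure* can be read as oversight. Section 5.13 provides a telephone call after 3 additional weeks of stimulation, a clinic visit at the end, prompt assessment and removal if stimulation is not tolerated, and reporting of unexpected adverse effects to the IRB. A reader should not infer that the extension is unmonitored. What stands is narrower: an event-free extension in so few children does not show that unanticipated harm is absent.

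**Conclusion.** The point holds. An open-label, uncontrolled extension limited to children who feel they respond cannot prove long-term efficacy, and this follows from the design whatever the size of the selection bias. Section 1.4 already words the goal appropriately; Aim 3 and outcome 3 go beyond it.

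The size and direction of the bias are conditional. It flatters the extension against weeks 1-2 only if entry depends on change from the baseline log, and is about zero there if entry is unrelated to the log or follows weeks 3-4 dryness alone. Against weeks 3-4 it runs the other way whenever entry depends on that log, more strongly under exact or level-only rules than under noisy ones. The percentages illustrate what is possible; they do not predict this study, because variability, entry rule, decision date and comparison period are all unstated. The model also omits spontaneous improvement and open-label reporting, either of which could add apparent benefit.

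The safety limit of 11% needs no assumption about wetting rates. It is the best case, since all 25 children would have to continue. Aims 1 and 2 are not affected by this selection.

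**What to change.** - Restate Aim 3 and main outcome 3, in line with section 1.4, as a description of durability and tolerability among children who chose to continue, with estimates and confidence limits and no claim of proof.
- Report the extension against both weeks 1-2 and weeks 3-4, and say that selection can push these two comparisons in opposite directions.
- Report how many of all enrolled children continued.

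This changes protocol wording and reporting only; it needs no extra visits, calls or children. The downside is a less favourable claim for the extension.
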